3.2 STUDY DURATION AND PACE OF ENROLLMENT

Total study duration is expected to be approximately 4 years. Recruitment is anticipated to be completed in 18 to 24 months. Individual study participation is 24 months.

3.3 STUDY ENDPOINTS

3.3.1 Primary Endpoint

The primary endpoint is an MMTT-stimulated 2 hour C-peptide AUC at week 52.

3.3.2 Secondary Endpoints

Efficacy:

1. MMTT-stimulated peak and 4 hour C-peptide AUC at weeks 52 and 104.
2. MMTT-stimulated 2 hour C-peptide AUC at week 104.
3. MMTT-stimulated 2-hour C-peptide AUC assessed longitudinally at weeks -2, 13, 26, 52, 78, and 104.
4. Insulin use in units per kilogram body weight per day at weeks 52 and 104.
5. Major hypoglycemic events, as defined in section 8.2.1, occurring from randomization at weeks 0, 52 and 104.
6. HbA1c levels at weeks 52 and 104.

Safety:

The rate of the following AEs in participants receiving imatinib or placebo:

1. Myelosuppression.
2. Gastrointestinal disorders.
3. Infections.
4. Hepatotoxicity.
5. Cardiac toxicity and edema.
6. Cutaneous reactions.
7. Muscle cramps, bone pain, arthralgias.
8. Fluid retention or peripheral edema.
9. Bone metabolism and growth abnormalities
10. Frequency and severity of all AEs in participants receiving imatinib or placebo.

3.3.3 Exploratory Endpoints

Mechanistic:

Immunological assessments described in section 7 will be compared with clinical outcomes to determine whether there is evidence of immune tolerance to diabetes-associated autoantigens.

Metabolic (see section 6.1.1 for further discussion):

1. Proportion of patients who are exogenous insulin-free (for at least 3 months) with an $HbA_{1C} \leq 6.5\%$ at weeks 52 and 104 in each treatment arm.
2. Proportion of subjects who achieve a persistent reduction (for at least 3 months) in insulin dose to < 0.5 units/kg at weeks 52 and 104 in each treatment arm.
3. Effects on insulin resistance will be evaluated using modeling from data obtained on MMTTs, and by assessing change in adiponectin, proinsulin levels (and proinsulin/c-peptide ratio), and glucagon.

3.4 RATIONALE FOR CLINICAL TRIAL DESIGN

The proposed trial will evaluate imatinib, a tyrosine kinase inhibitor, as a novel tolerance-inducing intervention in new-onset T1DM. As with ITN and TrialNet new-onset T1DM studies, endogenous insulin secretion will be assessed serially by measuring C-peptide AUC in response to a 4-hour MMTT. The proposed primary endpoint is a 2-hour C-peptide AUC in response to MMTT at week 52. This endpoint is in accord with an ADA workshop,¹⁷³ and the TrialNet consensus guidelines for new-onset T1DM studies. Other clinical outcome measures of efficacy include insulin use, HbA_{1C} , and major hypoglycemic events. The safety of patients in this study will be closely monitored, and expected adverse events related to imatinib have been selected as the secondary endpoints for safety (see section 3.3.2).

In accord with other ITN and TrialNet new-onset T1DM studies, we plan to randomly assign participants 2:1 (treatment vs. placebo). The greater chance of enrolling into a drug treatment arm has helped facilitate recruitment for such trials. Participants between ages 12 and 45 years will be recruited. T1DM can occur at any age, but it occurs with dramatically increased incidence in children. The average age of children at presentation of this disease is approximately 13 years, and most individuals present when they are under the age of 18 years. The incidence of T1DM is increasing at approximately 3% per year, mainly in the younger population.¹⁶⁵ Beta cell function declines faster in those < 21 years of age, relative to those > 21 (Greenbaum et al, Diabetes)¹⁷⁸. Many new-onset T1DM studies enroll up to age 45; the upper age limit is restricted in this study to 45 so that the trial will enrich for a group of subjects who are more likely to have a faster rate of decline in beta cell function, and therefore enable a more pronounced difference between those in the treatment versus placebo group, assuming the therapy will have an effect. Imatinib is approved for the treatment of chronic myeloid leukemia in children down to age 3 years. The dosing is adjusted for

body surface area, and the safety spectrum appears to be comparable to that in adults. Additional justification for the inclusion of children is presented in section 1.5.2.

We will treat participants within 100 days of their T1DM diagnosis. Past studies have suggested that subjects respond better with this earlier enrollment,^{29,36} and currently all recent-onset T1DM immunotherapy trials conducted by TrialNet, ITN, and many pharmaceutical studies enroll patients within 100 days of diagnosis^{36,38}. We have elected to have a 52-week primary endpoint for this trial, again in accord with ITN and TrialNet new-onset studies. It is important to consider whether the degree of C-peptide decline in the placebo group with optimal diabetes management is significant enough during the first year of diagnosis to detect a difference between the imatinib group and the placebo group. Steele et al. demonstrated that those with new-onset T1DM have steady, progressive loss in β -cell function from the time of diagnosis, as assessed by C-peptide AUC in response to an MMTT, the measure to be employed in this study.⁹ This finding has been corroborated by others in a series of new onset T1DM trials.^{27,34,36-39,174,175}

The metabolic and immunological / tolerogenic effect of imatinib will continue to be assessed during the follow-up phase (months 12–24). Preservation of C-peptide levels at the end of the follow-up phase in the imatinib group will be an indication of whether imatinib induces tolerance. A host of immunologic assays performed throughout the study will also provide insight into the mechanism of imatinib action and its possible tolerogenic properties (Refer to section 7 for a complete discussion of immunologic assays.)

3.5 RATIONALE FOR SELECTION OF DRUG, ROUTE, DOSE, AND REGIMEN

There have been a series of studies to define dose-response relationships with imatinib, beginning with the early phase 1 studies in CML.^{46,47,176} Doses between 200 to 300 mg/day appear to be on the steep part of the dose response curve. A dose that achieves concentrations of 1 μ mol/L, which inhibits Bcr-Abl kinase activity, appears to be optimal for inducing apoptosis, and these are the trough levels achieved in phase I studies of subjects on 260 mg/day. Thus, 260 mg has been considered a threshold dose for inducing optimal therapeutic responses. To ensure that the majority of treated subjects were above this threshold, 400 mg/day was adopted as the dose for phase II studies of patients with chronic disease, and with a half-life of 13–16 hours, once daily dosing was considered adequate. This dosing regimen has proven to be highly successful in treating CML and GIST.⁴⁴⁻⁴⁸ Doses higher than 400 mg/day may achieve better responses, particularly for those in accelerated and blast crisis studies. Doses of up to 1000 mg have been reached without convincing dose-limiting toxicity but, as noted above, the frequency and grade of adverse events increases, particularly above 600 mg/day.

The responses in autoimmunity noted above were achieved in subjects receiving at least 400 mg/day, and sometimes higher imatinib doses. Thus, 400 mg/day appears to be an effective dose in autoimmune diseases.

It is difficult to extrapolate exactly from the mouse dose employed by Louvet et al¹¹² to humans. They were successful with doses of 50 mg and 100 mg/kg and 1.5 to 3 mg/mouse, and ultimately used 1.5 mg/mouse. [name] considers this dose roughly comparable to 400 mg/day used in clinical studies (personal communication).

A common question with all studies is whether or not dose should be adjusted for a participant's size. Peng et al conducted a study to determine whether obesity had an effect on plasma levels of imatinib, and concluded that there was no evidence that patient size needed to be taken into consideration.¹⁷⁷ Deininger et al also reported that flat dosing was appropriate in a small number of obese subjects.¹²⁹ Considerations for children were reviewed in section 1.5.2, and we will follow the standard dosing of 260 mg/m² or 400 mg, whichever is lower, stated in the Gleevec package insert.

One additional consideration with regard to dosing is how long to continue drug therapy. Longer-term treatment (10 weeks versus 3 weeks) clearly resulted in a more robust and durable response in the NOD mouse. Based on this, we propose a 6-month treatment period—6 months strikes the appropriate balance between too short a period, with loss of long-term efficacy, and longer treatment (such as 12 months) with ongoing risk from the therapy. For its approved indications, Gleevec therapy is typically administered for years and even lifelong in some patients, but in this trial we will be assessing its role as a tolerizing agent after 6 months of therapy.

3.6 MEASURES TO MINIMIZE BIAS

The proposed trial has a double-blind design. One salient issue is whether or not the side effect profile will be such that it will serve to unmask a significant number of participants and study personnel. We expect that the side effects will be milder and less frequent than seen in oncology settings, as we will be enrolling a younger and healthier patient population who will be treated at the lowest therapeutic imatinib dose ([name], personal communication). Both the treatment and placebo groups will require close, regular monitoring, particularly during the treatment phase. Because endogenous insulin secretion is the primary outcome variable (i.e., C-peptide), and this in turn is affected by glycemic control, we will aim for comparable glycemic control in both groups, treating to established targets. The health care professionals managing T1DM will be blinded to treatment assignment.

3.7 STOPPING RULES

3.7.1 Ongoing Review

The progress of the study will be monitored by a Data and Safety Monitoring Board (DSMB), which will review safety data and make recommendations regarding

continuation, termination, or modification of the study. Based on an 18- to 24-month recruitment period and an additional study period of 24 months, the DSMB will formally review the safety data at least yearly. The number of subjects who discontinue study treatment will also be included in the reports prepared for the DSMB.

In addition, safety data will be reviewed by the DSMB when an event occurs that is of sufficient concern to the medical monitor, clinical trial physician, or protocol chairs to warrant review, or when an event occurs that contributes to a stopping rule listed in Section 5.3.

3.7.2 Stopping Rule Guidance

3.7.2.1 Study-related adverse events

If any of the following events occur, enrollment will be suspended and the DSMB chair will be notified such that a review of safety data will be conducted to determine if enrollment in the study will be stopped and/or administration of investigational study medication should be halted:

- Any death except those assessed as not related to study treatment on review by the protocol chairs, the clinical trial physician, and the medical monitor.
- One or more participants experience treatment-emergent, clinically significant cardiac toxicity.
- Two or more of the first 10 treated participants or $\geq 20\%$ of all treated participants experience a clinically significant, drug-related adverse event resulting in the permanent discontinuation of study treatment, as defined in section 5.3.
- If two or more of the first 10 treated growing-age participants, as defined in section 5.2.9, or greater than 20% of all treated growing-age participants, exhibit a decrease in Height Standard Deviation Score (Ht-SDS) of > 0.5 from baseline at 6 months, or > 0.8 from baseline at 12 months, then enrollment will pause for growing-age participants. Study enrollment will continue for participants who are not growing-age. DSMB review will determine whether imatinib treatment can resume in growing-age participants based on available growth and bone-metabolism data, as well as bone-age radiographs.

4. ELIGIBILITY

4.1 INCLUSION CRITERIA

Patients must meet *all* of the following criteria:

1. Males and females age 12–45 years of age who meet the ADA standard T1DM criteria.
2. Positive for at least one islet cell autoantibody (glutamate decarboxylase; insulin, if obtained within 10 days of the onset of insulin therapy; ICA 512-antibody; and/or ICA or ZnT8).
3. Diagnosis of T1DM within 100 days of Visit 0.
4. Peak stimulated C-peptide level >0.2 pmol/mL following an MMTT.
5. Participants of childbearing age who are sexually active must agree to use an effective form of birth control (e.g., barrier method, oral contraception, or surgery). For females, these contraceptive measures must be maintained throughout the study; for males these measures must be followed for a minimum of 3 months after discontinuation of imatinib therapy.

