Primary Endpoint	MMTT--stimulated 2 hour C-peptide AUC at week 52.
Secondary Endpoints	
Efficacy:
 
 • MMTT-stimulated peak and 4 hour C-peptide AUC at weeks 52 and 104.

- MMTT-stimulated 2 hour C-peptide AUC at week 104.
- MMTT-stimulated 2-hour C-peptide AUC assessed longitudinally at weeks -4, 13, 26, 52, 78, and 104.
- Insulin use in units per kilogram body weight per day at weeks 52 and 104.
- Major hypoglycemic events, as defined in section 8.2.1, occurring from randomization at weeks 0, 52 and 104.
- HbA1c levels at weeks 52 and 104

Safety:

- The rate of the following AEs in participants receiving imatinib or placebo:
 1. Myelosuppression.
 2. Gastrointestinal disorders.
 3. Infections.
 4. Hepatotoxicity.
 5. Cardiac toxicity and edema.
 6. Cutaneous reactions.
 7. Muscle cramps, bone pain, arthralgias.
 8. Fluid retention or peripheral edema.
 9. Bone metabolism and growth abnormalities (not including bone turnover markers).
 10. Frequency and severity of all AEs in participants receiving imatinib or placebo.

Mechanistic:

Immunological assessments described in section 7 will be compared with clinical outcomes to determine whether there is evidence of immune tolerance to diabetes-associated autoantigens.

Metabolic:

- Proportion of patients who are exogenous insulin-free (for at least 3 months) with an HbA1C \leq 6.5% at weeks 52 and 104 in each treatment arm.
- Proportion of subjects who achieve a persistent reduction (for at least 3 months) in insulin dose to $<$ 0.5 units/kg at weeks 52 and 104 in each treatment arm.
- Effects on insulin resistance as derived from data on MMTT, and change in adiponectin, proinsulin levels (and proinsulin/c-peptide ratio), and glucagon levels.

Inclusion Criteria

- Males and females age 12–45 years of age who meet the ADA standard T1DM criteria¹. Positive for at least one islet cell autoantibody.
- Diagnosis of T1DM within 100 days of Visit 0.
- Peak stimulated C-peptide level $>$ 0.2 pmol/mL following an MMTT at screening.
- Participants of childbearing age who are sexually active must agree to effective contraception. For females, these contraceptive measures must be maintained throughout the study; for males these measures must be followed for a minimum of 3 months after discontinuation of imatinib therapy.

- Exclusion Criteria**

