4.2 EXCLUSION CRITERIA

Patients must *not* meet any of the following criteria:

1. Prior history of any significant cardiac disease such as congestive heart failure, myocardial infarction, arrhythmia, or structural defects or suspicion thereof.
2. Leukopenia ($<3,000$ leukocytes/ μ L), neutropenia ($<1,500$ neutrophils/ μ L), or thrombocytopenia ($<125,000$ platelets/ μ L).
3. Low Hemoglobin (baseline hemoglobin below the lower limit of normal)
4. Prior history of anaphylaxis, angioedema or serious cutaneous drug reactions
5. Any sign of significant chronic active infection (e.g., hepatitis, tuberculosis, EBV, CMV, or toxoplasmosis), or screening laboratory evidence consistent with a significant chronic active infection (such as positive for HIV, PPD/IGRA, or HB_sAg). Significant acute infections must be resolved before treatment may commence, e.g., acute respiratory tract, urinary tract, or gastrointestinal tract infections.
6. Anticipated ongoing use of diabetes medications other than insulin that affect glucose homeostasis, such as metformin, sulfonylureas, thiazolidinediones, glucagon-like peptide 1 (GLP-1) mimetics, dipeptidyl peptidase IV (DPP-IV) inhibitors, or amylin.
7. Prior or current treatment that is known to cause a significant, ongoing change in the course of T1DM or immunologic status, including high-dose inhaled, extensive topical or systemic glucocorticoids.

8. Evidence of liver dysfunction, with alanine aminotransferase (ALT) or aspartate aminotransferase (AST) >2.0 times the upper limit of normal persistent for 1 week or greater.
9. Evidence of renal insufficiency as indicated by serum creatinine of >1.2 times the upper limit of normal confirmed in a repeat test at least 1 week apart.
10. Evidence of clinically significant metabolic bone disease (except adequately treated rickets).
11. Females who are pregnant at the time of screening, breastfeeding or unwilling to defer pregnancy during the 24-month study period. (Female participant must be at least 100 days postpartum before enrollment into study).
12. Prior treatment with imatinib or related tyrosine kinase inhibitor.
13. Unable to avoid medications that affect CYP3A4: either inducers that may decrease imatinib levels, or inhibitors that may increase drug concentrations. (Refer to section 1.5.1.12 for a complete list of inducers and inhibitors.)
14. Height standard deviation score ≥ 2 standard deviations below mean (participants of growing-age potential)

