5.2.8 Pregnancy

Site staff will regularly review the concerns regarding avoidance of pregnancy with participants during the course of the study, especially during the initial 6 months on therapy. Urine pregnancy tests will be conducted at baseline and every following visit while on study drug. Male participants are to use birth control at least 3 months after study drug discontinuation. If, despite these measures, a participant becomes pregnant, imatinib will be permanently discontinued and the participant will be counseled on potential risks to the fetus. Pregnancies of partners of male participants will also be followed.

Given the potential risk to the fetus, while on study drug/placebo, women of child-bearing potential, defined as all women physiologically capable of becoming pregnant, must agree to use highly effective methods of contraception.. This contraception should start 1 week or more prior to the start of study drug/placebo (noting that the terminal half-life of imatinib is approximately 18 hours, and 5 times this duration is 90 hours or ~4 days)) and continue during the subsequent 6 months of study drug/placebo dosing ***Highly effective contraception methods include:***

- Total abstinence (when this is in line with the preferred and usual lifestyle of the subject). Periodic abstinence (e.g., calendar, ovulation, symptothermal, post-ovulation methods) and withdrawal are not acceptable methods of contraception
- Female sterilization (have had surgical bilateral oophorectomy with or without hysterectomy) or tubal ligation at least six weeks before taking study treatment. In case of oophorectomy alone, only when the reproductive status of the woman has been confirmed by follow up hormone level assessment
- Male sterilization (at least 6 months prior to screening). For female subjects on the study the vasectomized male partner should be the sole partner for that subject
- Combination of any two of the following (a+b or a+c, or b+c):
 - a. Use of oral, injected or implanted hormonal methods of contraception or other forms of hormonal contraception that have comparable efficacy (failure rate <1%), for example hormone vaginal ring or transdermal hormone contraception
 - b. Placement of an intrauterine device (IUD) or intrauterine system (IUS)

- c. Barrier methods of contraception: Condom or Occlusive cap (diaphragm or cervical/vault caps) with spermicidal foam/gel/film/cream/vaginal suppository

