6.2 RANDOM ASSIGNMENT, BLINDING, AND UNBLINDING

6.2.1 Random Assignment

Participants who sign the informed consent and meet the eligibility criteria will be randomly assigned in a 2:1 ratio to either the experimental or control group. A central automated randomization system will be used for treatment assignment and to create a unique identifier for each new study participant. Random assignment will be stratified according to site.

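### Inclusion item 5 lets a woman enter on one contraceptive method without citing the stricter rule in 5.2.8, and Appendix 1 omits the week-2 pregnancy test that 5.2.8 requires

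*Combined protocol and SAP*

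**What the plan says.** **Entry criteria.** Section 4.1 item 5 applies to sexually active participants of childbearing age, men and women alike, and requires "an effective form of birth control (e.g., barrier method, oral contraception, or surgery". Women must continue throughout the study, and men for at least 3 months after stopping imatinib. The synopsis is shorter: "Participants of childbearing age who are sexually active must agree to effective contraception". Section 4.2 item 11 excludes "Females who are pregnant at the time of screening, breastfeeding or unwilling to defer pregnancy during the 24-month study period" and sets no contraceptive standard. Section 6.2.1 provides that participants who have signed consent and "meet the eligibility criteria will be randomly assigned in a 2:1 ratio".

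**Section 5.2.8.** While on study drug or placebo, women of child-bearing potential "must agree to use highly effective methods of contraception". The accepted options are total abstinence, female sterilization, a sterilized sole male partner, or "Combination of any two of the following (a+b or a+c, or b+c", where a is hormonal, b is an IUD or IUS, and c is a barrier with spermicide. On timing: "This contraception should start 1 week or more prior to the start of study drug/placebo". It continues through the 6 months of dosing. Pill users must have been stable on the same pill for 3 months before treatment.

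**Testing.** Section 5.2.8 states: "Urine pregnancy tests will be conducted at baseline and every following visit while on study drug". Section 8.2.1 has the investigator establish female participants' pregnancy status at each visit. In Appendix 1, the Urine hCG and Pregnancy Monitoring rows are both blank at Visit 1 (week 2).

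**The concern.** The protocol states two contraceptive standards for the same women and puts the weaker one where eligibility is decided. A site that screens from section 4 and tests from Appendix 1 would apply less protection than 5.2.8 intends. The shortfall is hard to repair after randomisation, because 5.2.8 methods must be in place at least 1 week before drug and Appendix 1 shows drug starting at Visit 0.

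Section 1.5.1.10 explains why this matters. Imatinib is teratogenic in rats but not rabbits. Rats show post-implantation loss at a dose the protocol equates to 400 mg/day, which is this trial's adult dose (5.1.2). The drug is in pregnancy class D. In the largest human series cited, 125 exposed pregnancies had known outcomes and 12 infants had abnormalities, 3 of them with a similar pattern. The section also says that most exposed fetuses appear unaffected. It concludes that investigators must make sure participants avoid pregnancy.

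**Working it through.** No statistical figure is involved. The check sets the texts side by side and counts visits.

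**Step 1. Contraceptive standard.**

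| | 4.1 item 5 | 5.2.8 |
|---|---|---|
| Who | Sexually active, of childbearing age, either sex | Women physiologically able to conceive |
| Minimum | One effective method | Abstinence, sterilization, or two of hormonal, IUD/IUS, barrier |
| Start | Not stated | At least 1 week before drug; 3 months on the same pill for pill users |
| End (women) | End of study (week 104) | End of the 6 months of dosing |
| Reference to the other section | None | None |

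Taking item 5's three examples in turn, **for a woman**:

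- Barrier alone: meets item 5, fails 5.2.8.
- Oral contraception alone: meets item 5, fails 5.2.8.
- Surgery: meets item 5, and can meet 5.2.8 as sterilization.

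For a man none of the three conflicts with 5.2.8, whose two-method rule is written for women. The protocol does use cross-references in its eligibility list elsewhere: 4.2 item 13 points to 1.5.1.12 for the list of interacting drugs. Item 5 has no such pointer.

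**Step 2. Pregnancy tests on drug.** Inputs are the Study drug administration and Urine hCG rows of Appendix 1 and the windows in 6.3.1.

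- Visits marked for study drug: weeks 0, 2, 4, 9, 13, 17, 22, 26, which is 8 visits.
- Of these, urine hCG is marked at weeks 0, 4, 9, 13, 17, 22, 26, which is 7 visits. Week 2 is the only one missing.
- Column check: the ECG row is marked at Visits -1 and 1, as 5.2.10 requires, so the week-2 column is being read correctly.
- Gaps between on-drug tests: (4 − 0) × 7 = 28 days, (9 − 4) × 7 = 35, (13 − 9) × 7 = 28, (17 − 13) × 7 = 28, (22 − 17) × 7 = 35, (26 − 22) × 7 = 28.
- First post-baseline test: day 28 ± 7, or days 21 to 35, as scheduled. Under 5.2.8 it would be day 14 ± 3, or days 11 to 17.

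Week 39 is also blank in both rows. That visit is off drug, so 5.2.8 does not require a test there; only the each-visit wording of 8.2.1 reaches it.

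**Step 3. Status at first dose.** Exclusion 11 names pregnancy at screening, and Appendix 1 marks the eligibility check only at Visit -1. That visit is 14 to 28 days before Visit 0 by 6.3.1, or 21 to 28 days by the Appendix 1 column heading. A urine hCG is scheduled at Visit 0, 8.2.1 requires status to be established at each visit, and 5.2.8 and 5.3 stop drug if pregnancy occurs. What no sentence fixes is the order: that the Visit 0 result is read as negative before randomisation and the first dose.

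**The case against.** The strongest reply is that 5.2.8 is itself binding. It says what women of child-bearing potential must agree to, and it takes effect before dosing. A site following the whole protocol applies both sections, and the stricter governs during treatment. That is right, and it means the sections can be satisfied together: 5.2.8 methods during dosing, then an effective method to week 104. A reader might infer an irreconcilable conflict; the documents do not support that.

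Consent is also half of the gate in 6.2.1. The consent pages are not in the available copy, so nothing can be said about whether agreement to 5.2.8 is obtained there. The point is confined to section 4 and the synopsis.

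A reader might also infer that the protocol lets a pregnant woman be dosed unchecked. It does not: the Visit 0 test, 8.2.1 and the stopping rules in 5.2.8 and 5.3 cover that case, and only the sequence is left unstated. Nor does the missing week-2 test open an unusually long unmonitored stretch, since the schedule accepts 35-day gaps twice on drug. Finally, two of item 5's three examples fall short for women only; item 5 is one list for both sexes.

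What survives is that two written rules differ on who may enter and on when women are tested, and that eligibility and scheduling rest on the weaker one.

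**Conclusion.** The point holds as a minor safety-consistency correction that should be made.

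- **Method.** For women of child-bearing potential, item 5 and the synopsis can be met by a barrier or a pill alone, which 5.2.8 does not accept. The fault is a missing cross-reference at the point of entry.
- **Testing.** Appendix 1 covers 7 of 8 on-drug visits where 5.2.8 requires all 8. The practical effect is modest, because the 28-day gap equals the shortest interval between the other on-drug tests.
- **Visit 0.** The order of test, randomisation and first dose needs clarifying; this is not a missing safeguard.

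The conclusion rests on the text of 4.1, 5.2.8, 6.2.1 and 8.2.1, and on Appendix 1 as read with the ECG row as an alignment check. The documents give no number of women of child-bearing potential, so no count of exposed pregnancies is claimed. There is no effect on power or type I error.

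**What to change.** 1. In 4.1 item 5 and the synopsis line, require women of child-bearing potential to meet 5.2.8, including its 3-month stable-pill condition, from at least 1 week before Visit 0 through dosing, and then to use an effective method to week 104. Leave the rule for men unchanged.
2. In Appendix 1, mark Urine hCG and Pregnancy Monitoring at Visit 1.
3. As a clarification, state in 4.2 item 11 or 5.2.8 that the Visit 0 urine hCG must be read as negative before randomisation and first dose.

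The cost is wording in a few lines, two table cells, and one extra urine test per woman at a visit already held. Women on a single method must add a second before entry, which 5.2.8 already requires before dosing. A pill first started at screening, at most 28 days before Visit 0, cannot satisfy the 3-month condition. A barrier-only user would therefore need an IUD/IUS or a non-oral hormonal method, while an established pill user can add a barrier. Because entry must fall within 100 days of diagnosis, sites should raise this at first contact.
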